14.6.8 Secondary Endpoint #8

Seizure freedom (defined as Engel Class I, Appendix C) at 12 months following the Visualase procedure compared to historical control for open surgical resection

[figure not shown]
It is hypothesized that the seizure freedom at 12 months following the Visualase procedure will not be inferior to 64% reported in the literature for open surgical resection.

Null Hypothesis: $\pi \text{ (V-SF} - 64\%) + \delta \leq 0$ Alternate Hypothesis: $\pi \text{ (V-SF} - 64\%) + \delta > 0$

Where π (V-SF – 64%) is the proportion of subjects treated with Visualase experiencing no seizures.

An exact 95% confidence interval for the percentage of subjects who are seizure free will be calculated and its lower boundary compared to zero after subtraction of the historical open surgical resection percentage of 64% and the addition of the equivalence delta percentage of 10%.

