Two surgical resection techniques have been commonly utilized to treat mesial temporal epilepsy, namely anterior temporal lobectomy with mesial temporal resection (ATL) and selective amygdalohippocampectomy (SAH). Schramm reviewed 53 studies in which various temporal lobe resections were performed for medically intractable mesial temporal lobe epilepsies and found consistently high rates of seizure freedom at oneyear post-operative follow-up.9 In the most referenced randomized TLE study by Wiebe et al, seizure freedom occurred in 58% of the group assigned to surgery versus 8% for the patients who continued with medical therapy only. 10 A second randomized trial provided confirmation of these results; 73% of mesial TLE patients who underwent temporal lobe resection were seizure-free after 2 years compared to 0 patients with medical treatment. 11 Despite these, and many other well-documented high rates of seizure-freedom following surgical resection of temporal foci, the utilization of temporal lobectomy has not increased from 1990 to 200812 but has decreased, according to a recent survey. 13 Not only has surgery for epilepsy remained arguably the most underused of all proven effective therapies, even those patients who are referred for surgery wait for an average of 22 years after onset of epilepsy for that referral, 14 often too late to prevent or reverse the disabling adverse medical, psychological and social consequences of recurrent seizures. Factors like prolonged recovery, surgical invasiveness, and potential morbidities such as neurological deficits have been obstacles for completion of more epilepsy surgeries.

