14 STATISTICAL METHODS AND DATA ANALYSIS

14.1 Sample Size Determination

Subjects will be considered enrolled upon the signing of a consent form. It is anticipated that once enrolled, some subjects will not proceed to the Visualase procedure due to failure at their pre-surgical evaluation, changes in clinical status, or non-compliance to protocol. Based on these factors, and on previous reports of attrition in similar studies, the assumed attrition rate is 30%. To account for this attrition, up to 215 subjects may be enrolled to ensure at least 150 subjects are treated with the Visualase procedure.

The primary efficacy endpoint is the 12-month seizure-free rate. The analysis of the primary efficacy endpoint will include a point estimate and exact 95% confidence interval (CI) of the rate. The lower bound of the 95% CI of the seizure freedom rate following the Visualase procedure must be above 43%. Based on published and unpublished accounts of seizure freedom rates following laser ablation for MTLE, it is expected that approximately 56% of subjects who undergo the Visualase procedure will be seizure free through 12 months post procedure. Given these assumptions, 89% power can be achieved with data from 150 treated subjects.

Certain secondary endpoint assessments will be made using subject questionnaires. These self-reported instruments are influenced by primary language. Validated translations are not available in all languages, thus enrollment will be limited to subjects who can complete these assessments in either English or Spanish. Further, the impact of grouping across translations for analysis is an important consideration. Therefore, for the specified secondary cognitive and QOL endpoints, the subset of only the Englishlanguage versions will be used for analysis. To preserve adequate statistical power for analysis of this subset, the total Spanish language enrollment will be restricted to no more than 40% of the total study-wide enrollment population.

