14.2 General Considerations

Statistical analyses will be performed using SAS Software, Version 9.4 or later.

All statistical tests will be conducted at a two-sided alpha level of 0.05 unless otherwise stated.

A Statistical Analysis Plan (SAP) will include a comprehensive description of the statistical methods and reports to be included in the final study report. Any change to the analysis methods described in the protocol will require an amendment only if it changes a principal feature of the protocol. Any other change to the analysis methods described in the protocol, and the justification for making the change, will be described in the clinical study report.

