7.9.3.8 Secondary Endpoint #8

Seizure freedom (defined as Engel Class I, Appendix 1) at 12 months following the Visualase procedure compared to historical reference threshold for open surgical resection

[figure not shown]
It is hypothesized that the seizure freedom at 12 months following the Visualase procedure will not be inferior to 64% reported in the literature for open surgical resection (Wiebe 2001). The hypotheses associated with this endpoint are as follows:

[figure not shown]
Null Hypothesis: $\pi V - 64\% + \delta \le 0$ Alternate Hypothesis: $\pi V - 64\% + \delta > 0$

Where πV is the proportion of subjects treated with Visualase experiencing no seizures.

An exact 95% CI for the percentage of subjects who are seizure free will be calculated and its lower boundary compared to zero after subtraction of the historical open surgical resection percentage of 64% and the addition of the equivalence delta percentage of 10% (Wiebe 2001).

[figure not shown]

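### Secondary endpoint 8 is worded as non-inferiority to open resection, but its one-sample test supports only a seizure-free rate above a fixed 54%

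*Protocol*

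**What the plan says.** Protocol 14.6.8 presents endpoint 8 as seizure freedom set against a historical control for open resection. SAP 7.9.3.8 keeps the endpoint but describes it as "compared to historical reference threshold for open surgical resection". Both carry the same hypothesis; in the SAP's words, Visualase "will not be inferior to 64% reported in the literature for open surgical resection".

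The method is also the same in both. Protocol 14.6.8: "An exact 95% confidence interval for the percentage of subjects who are seizure free will be calculated", with "its lower boundary compared to zero after subtraction of the historical open surgical resection percentage of 64% and the addition of the equivalence delta". SAP 7.9.3.8 gives the margin as "the addition of the equivalence delta percentage of 10" percent. Neither document gives a denominator, standard error or interval for the 64%, and no step carries its uncertainty.

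The SAP cites the 64% to a randomised surgery trial. Protocol 3.1 describes the same trial and reports 58% seizure freedom in the group assigned to surgery. It then reports from a second randomised trial that "73% of mesial TLE patients who underwent temporal lobe resection were seizure-free after 2 years".

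On error control, Protocol 14.2 says: "All statistical tests will be conducted at a two-sided alpha level of 0.05 unless otherwise stated". Endpoint 8 is the last of eight in a fixed sequence and is tested only if the primary efficacy endpoint and secondary endpoints 1 to 7 all succeed (Protocol 14.6, SAP 7.5). SAP section 5 acknowledges that there is no active control arm.

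**The concern.** The conclusion and the calculation concern different quantities. Non-inferiority to open resection is a statement about the Visualase rate minus the resection rate. The interval describes the Visualase rate alone and then shifts it by a constant. The 64% is an observed proportion taken from the literature, so it has sampling error of its own. The protocol's background section also shows that published resection rates differ.

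Endpoint 8 is the only formally tested comparison of seizure freedom with a published open-resection rate. If it passes, the natural summary is that laser ablation was shown non-inferior to open resection with 95% confidence. The method does not supply that confidence, and neither document limits the conclusion to what the method does supply.

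**Working it through.** **Inputs.** N = 150 treated, expected rate 56% and primary threshold 43% (Protocol 14.1); reference 64% and margin 10 points (Protocol 14.6.8, SAP 7.9.3.8); two-sided alpha 0.05 (Protocol 14.2). Assumptions: the exact interval is Clopper-Pearson, which the documents name only for the safety endpoint; all 150 outcomes are observed; the size m of the group behind the 64% is not in the documents and is varied.

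**1. Reproduce the plan's own figure.** The Clopper-Pearson lower limit L(x) is the 0.025 quantile of Beta(x, 150 − x + 1). The smallest x with L(x) > 0.43 is 77. P(X ≥ 77 | 150, 0.56) = 0.891, which matches the protocol's "89% power can be achieved with data from 150 treated subjects". No power or error rate is stated for endpoint 8.

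**2. Endpoint 8 as written.** Pass if L(x) − 0.64 + 0.10 > 0, that is L(x) > 0.54.
- L(93) = 0.537 and L(94) = 0.544, so the bar is 94/150 = 62.7%.
- One-sided error against a fixed 54%: P(X ≥ 94 | 150, 0.54) = 0.0198.
- Chance of passing, before any gating: 66.7% if the true Visualase rate is 64%, and 5.8% at the planned 56%.

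**3. The same rule read as a comparison with the resection rate.** Let the true rates be 64% (resection) and 54% (Visualase), exactly at the margin, and let the published reference be y/m with y ~ Bin(m, 0.64). Writing r(t) for the smallest count with L > t,

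false non-inferiority = Σ over y of Bin(y; m, 0.64) × P(X ≥ r(y/m − 0.10) | 150, 0.54).

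The table also shows the Newcombe 95% lower limit for the difference at the minimum pass (94/150 against an observed 64%), and the count needed under a two-sample unpooled Wald interval with its lower limit above −10 points.

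| Assumed m | False non-inferiority, written rule | Newcombe lower limit at 94/150 (points) | Two-sample bar |
|---|---|---|---|
| 40 | 17.0% | −16.6 | 106/150 |
| 100 | 9.8% | −13.2 | 100/150 |
| 300 | 4.9% | −10.9 | 96/150 |
| 1000 | 2.8% | −9.8 | 94/150 |

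Bar at m = 300: 96/150 = 0.64, so the difference is 0; SE = √(0.64×0.36/150 + 0.64×0.36/300) = 0.048; lower limit = −1.96 × 0.048 = −0.094. At 95/150 the lower limit is about −0.101, which fails.

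Normal cross-check at m = 100: s_V = √(0.54×0.46/150) = 0.0407 and s_R = √(0.64×0.36/100) = 0.048. Then 1 − Φ(1.96 × 0.0407 / √(0.0407² + 0.048²)) = 1 − Φ(1.27) ≈ 10.2%, close to the exact 9.8%.

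These rates ignore the testing sequence. Requiring the earlier endpoints to succeed can only lower them, so for each m they are upper bounds.

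**4. Dependence on the reference figure.** With the margin held at 10 points, a 58% reference gives a threshold of 58 − 10 = 48% and a bar of 85/150. The 64% reference gives 94/150. The two figures attached to one trial therefore move the bar by 9 subjects.

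**The case against.** The strongest reply is that the hypothesis concerns a number. Both documents say not inferior to the 64% in the literature, the SAP null is written as the Visualase rate minus 64% plus the margin, and the SAP calls the comparator a reference threshold. Read that way, the exact interval is the right one and its error is 1.98%, below the nominal 2.5%. The 8%, 40% and 43% comparisons have the same fixed-goal structure, and the SAP admits there is no control arm. This stands: against the literal threshold there is no inflation. It does not settle the wording, because the same SAP section keeps the open-resection comparison, a non-inferiority hypothesis and a margin, and nothing restricts what a pass may be said to show.

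A reader might go further and infer that the false non-inferiority rate is several times 2.5%. The documents do not support that as a flat statement. It holds only if the 64% comes from a fairly small group: by the normal approximation, at least threefold up to about 160 patients, under twofold above about 330, and near nominal at 1000. The calculation also redraws the reference in every hypothetical trial, whereas here 64% is fixed in advance. If the true resection rate is 64% or lower, a treatment 10 points worse passes at most about 2% of the time. The exposure is to 64% being too low.

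A reader might also take the 73% as evidence that it is too low. That figure is at 2 years rather than 12 months, and the 58% in the same section points the other way.

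Finally, the practical reach is limited. The endpoint is last in the sequence, no other test depends on it, and at the planned 56% it would pass only about 5.8% of the time.

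**Conclusion.** The point holds as a mismatch between conclusion and test. A pass on endpoint 8, at 94/150 or more, supports a seizure-free rate above 54% and nothing stronger. The level of that test is correct (1.98%, assuming Clopper-Pearson and 150 complete outcomes). It does not support non-inferiority to open resection as a treatment, because the reference's sampling error is left out.

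The size of that omission cannot be fixed from the documents. It runs from about 17% at an assumed reference size of 40 to 2.8% at 1000, as upper bounds before gating on the earlier endpoints, with true rates of 64% and 54%.

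One part needs no assumption: the SAP attributes 64% to a trial for which Protocol 3.1 reports 58%, and the pass bar depends on which figure applies. The primary endpoint and the other secondary tests are unaffected.

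**What to change.** 1. Reconcile the 64% in SAP 7.9.3.8 with the 58% in Protocol 3.1. State the source, the outcome definition, the count and the denominator, and do so before outcome data are analysed.

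2. Keep the one-sample test, but restate the hypothesis and permitted conclusion in Protocol 14.6.8 and SAP 7.9.3.8 as the seizure-free rate exceeding a fixed performance goal of 54%, derived as 64% minus 10 points. Drop the claim of non-inferiority to open resection, and align the endpoint titles in the protocol synopsis, Protocol 6.2.3 and SAP 4.2.3. If step 1 changes the 64%, the goal changes with it. The cost is wording only: no patients, no data, and no effect on any other test.

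3. If the non-inferiority claim is to be kept, replace the one-sample rule with a two-sample 95% interval (Newcombe or Miettinen-Nurminen) for Visualase minus resection, using the reconciled count and denominator, and require a lower limit above −10 points. This cannot be run until step 1 is done. It costs a few lines of SAP text and one calculation, but the bar rises if the source is small. Under the Wald version above, the chance of passing at a true 64% falls from 66.7% to 27.8% with a reference group of 100, and to 5.1% with 40. It would still not address whether a historical group is comparable with this trial's subjects.

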14.8 Interim Analysis

No formal interim analysis is planned. Any unplanned interim analyses will be conducted under the auspices of the DMC assigned to this study. The DMC is authorized to review interim efficacy and safety analyses and, if necessary, to disseminate those results. The DMC will release interim results only if necessary to ensure patient safety. Any such release will be documented and described in the final study report. Study sites will not receive interim results unless they need to know for the safety of their patients.

14.9 Missing Data

Missing primary efficacy endpoint values and missing secondary endpoint values associated with testable hypotheses will be imputed for analysis with the mITT analysis population. The primary method of imputation will be by multiple imputation (SAS PROC MI and MIANALIZE) using the Markov chain Monte Carlo method. Details of predictor variables to be used in SAS PROC MI, seed number, and number of imputations to be performed will be provided in the SAP.

14.10

15 DATA AND QUALITY MANAGEMENT

15.1 Documentation Confidentiality and Accessibility

Documentation provided and generated as a result of this study is considered confidential and governed by the terms of the Confidentiality and Study Agreements. Access to and collection of medical records and subject data for this study is governed by the terms of the ICF and HIPAA release authorization.

All records and other information about subjects participating in this study will be treated as confidential. Data will be transferred and processed by Medtronic or a third party designated by Medtronic in a key coded form, unless it's impossible to make it anonymous.

The Sponsor or a regulatory authority may audit or inspect the study site to evaluate the conduct of the study. The clinical Investigator(s)/institution(s) must allow study-related monitoring, audits, IRB review and regulatory inspection by providing direct access to source data/documents.

15.2 Data Collection

Data will be collected using an electronic data management system for clinical trials. The electronic data management system will be compliant with the provisions in the Code of Federal Regulations Title 21 Part 11 for Electronic Records. Electronic CRF data will be stored in a secure, password-protected database which will be backed up routinely. Data will be reviewed using programmed and manual data checks. Data queries will be made available to sites for resolution. Study management reports may be generated to monitor data quality and study progress, including subject compliance.

At the end of the study, the data will be frozen and will be retained per Medtronic policies. The data reported on the eCRFs must be derived from source documents and be consistent with these source documents, and any discrepancies must be explained in writing.

15.3 Study Documentation

The Sponsor is responsible for the development, distribution, maintenance and long-term storage of study documentation. Pre-study documentation includes the core study protocol, CRF templates, CRF instructions, visual aids, and other study-specific materials. Intra- and post-study documentation includes archived versions of study protocols, CRF templates, original completed CRFs, CRF instructions, visual aids, source documents and other study-specific materials.

The data reported on eCRFs must be derived from source documents and be consistent with these source documents. Any discrepancies must be explained in writing.

15.4 Data Flow

Investigational sites are responsible for notifying the Sponsor of new subject enrollments using the appropriate notification system. Notice to the Sponsor of the entry of a subject in the study is the indicator that data will be expected at the intervals prescribed in this protocol.

15.5 Data Transmission and Entry

Data will be entered into the database at the intervals prescribed in this CIP (Section 7.7). Completed eCRFs and required file uploads will be forwarded to the Sponsor, or their designee.

15.6 Data Edits

Data edits will be performed using industry recognized methods, for which an acceptable audit trail exists to record all data alterations. As required, all queries for data verification/correction will be completed by the designated study personnel and include approval by the Investigator. The data editing process includes, but may not be limited to:

- Review of the CRFs will be conducted by the Sponsor, and manual edit checks may be added
- The Data Manager will check for discrepancies that can be corrected using Global Rule
- Automated edit checks will fire upon data entry, generating Data Clarification Forms (DCFs) for site verification/correction
- At periodic intervals, data validation activities will be performed to assess the completeness and accuracy of the data
- Clean and frozen data will be translated into the appropriate file type for data analysis

15.7 Electronic Medical Records

For sites using electronic medical records, the Sponsor may request that the study site designee print original source documents and verify that the record is a true reproduction of the original source document by initialling and dating the hard copy. Any discrepancies must be explained in writing.

16 REQUIRED RECORDS AND REPORTS

16.1 Investigator Records

The Investigator is responsible for the preparation and retention of the records cited below. All of the records listed below, with the exception of case history records and CRFs, should be kept in the Investigator site file or subject study binder. CRFs must be maintained and signed electronically within the electronic data capture system during the study. The following records are subject to inspection and must be retained for a period

of two years (or longer as local law or hospital administration requires) after product approval or the date on which the investigation is terminated or the date that the records are no longer required for purposes of supporting a pre-market approval application. Medtronic requires notification in writing if the Investigator wishes to store study documents off-site or to relinquish the study data records so that mutually agreed-upon arrangements can be made for transfer of the data records to a suitably qualified, responsible person.

- All correspondence between the IRB, sponsor, monitor, FDA, and the Investigator that pertains to the investigation, including required reports
- Subject's case history records, including:
 - Informed consent form signed and dated by subject and Investigator or designee
 - Observations of AEs/ADEs/device deficiencies
 - Medical history
 - Visualase procedure and follow-up data
 - Documentation of the dates and rationale for any deviation from the protocol
- Financial disclosure
- Subject log
- All approved versions of the CIP, ICF, and Report of Prior Investigations Summary
- Signed and dated Investigator agreement
- Current curriculum vitae of principal investigators and key members of investigational site team
- Documentation of delegated tasks
- IRB approval documentation. Written information that the Investigator or other study staff, when member of the IRB, did not participate in the approval process
- Study training records for site staff
- Any other records that FDA requires to be maintained (e.g., financial disclosure)
- Final Study Report including the statistical analysis

16.2 Investigator Reports

The Investigator is responsible for the preparation (review and signature) and submission to the sponsor of all CRFs, AEs, device deficiencies, deaths, and any deviations from the CIP. If any action is taken by an IRB with respect to this clinical study, copies of all pertinent documentation must be forwarded to Medtronic in a timely manner. Reports are subject to inspection and to the retention requirements as described above for investigator records.

The Investigator must prepare and submit in a complete, accurate, and timely manner the reports listed in this section.

Table 8: Investigator Reports per FDA Regulations

Report	Submit to	Description/Timing
UADE	Sponsor and IRB	The Investigator shall submit to the sponsor and to the reviewing IRB a report of any UADE occurring during an investigation as soon as possible, but in no event later than 10 working days after the investigator first learns of the effect. (21 CFR 812.150(a)(1))
Withdrawal of IRB Approval (either suspension or termination)	Sponsor	The Investigator shall report a withdrawal of approval by the reviewing IRB of the investigator's part of the investigation within 5 working days. (21 CFR 812.150(a)(2))
Progress Report	Sponsor and IRB	The Investigator shall submit this report to the sponsor and IRB at regular intervals, but in no event less than yearly. (21 CFR 812.150 (a)(3)).
Study Deviations	Sponsor and IRB	Notice of deviations from the CIP to protect the life or physical well-being of a subject in an emergency shall be given as soon as possible, but no later than 5 working days after the emergency occurred. Except in such an emergency, prior approval by the sponsor is required for changes in or deviations from a plan. If these changes or deviations may affect the scientific soundness of the plan or the rights, safety or welfare of human subjects, FDA and IRB must also be notified. (21 CFR 812.150(a)(4))
Failure to Obtain Informed Consent (prior to investigational device use)	Sponsor and IRB	If an Investigator uses a device without obtaining informed consent, the investigator shall report such use within 5 working days after device use. (21 CFR 812.150(a)(5))
Final Report	Sponsor and IRB	This report shall be submitted within 3 months of study completion or termination of the investigation or the investigator's part of the investigation. (21 CFR 812.150(a)(6))
Other	IRB and FDA	An Investigator shall, upon request by a reviewing IRB, FDA or any other regulatory agency, provide accurate, complete, and current information about any aspect of the investigation. (21 CFR 812.150(a)(7))

